The long-term course of anorexia nervosa is heterogeneous, and in some patients the disorder shows a protracted course, with long term morbidity and functional impairment, as well as increased mortality (11). There are few longitudinal studies of treatment outcomes with long follow-up periods (12). As Norway has a general system of personal identification numbers, following up patients across multiple public registries is a viable way to assess long term outcomes without the patients needing to participate in reporting.

AIMS

The primary aim is to assess the short and long-term effectiveness of FBT compared with non-manualised family therapy. This is operationalised as testing whether the adoption of FBT has led to patients achieving normalisation of weight faster than with the previously delivered family therapy, and whether it will lead to less treatment provided for eating disorders in adulthood. Secondary aims are to assess whether adoption of FBT have resulted in reduced time to discharge, changed the heterogeneity of weight gain across patients, whether there have been changes in the rates of adverse events and readmissions, and to assess whether the implementation of FBT has led to changes in long-term functional status and rate of mortality.

DESIGN AND METHODS

Participants and recruitment

This is a two-group retrospective exploratory cohort study with prospective longitudinal follow-up in public registries. Eligible participants are all patients initiating treatment during the years 2015-2020 with the eating disorder team at Nedre Romerike BUP with a primary ICD-10 diagnosis of F50.0 Anorexia nervosa or F50.1 Atypical anorexia nervosa. Patients will be excluded if they were treated during the years 2018-2020 and FBT was never initiated. It is estimated that the final sample size will be approximately 200.

Eligible participants will be identified through review of patient health records. Participants will be contacted by letter with information about the study, including a link to an online video explaining more about the study. Study personnel will make a follow-up telephone call approximately a week later to allow the eligible participant to ask any questions they may have before deciding on participation in the study. Participants who are interested in participating will be directed to a website

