where they can sign an electronic consent form and complete a short survey about their experience of treatment. The consent form and treatment experience survey will be implemented in “Tjenester for Sensitive Data”, which has appropriate security and allows for verified electronic signatures.

Participants will be contacted after they have reached age 16, and thus are able to give informed consent. They will be encouraged to discuss participation with their parents or other legal guardians.

Endpoints and data collection

Primary endpoint for the retrospective study is weight restoration, defined by patients having a weight measurement placing them at or above 95% of expected body weight (50. percentile) for age given Norwegian population norms, following established definitions of weight restoration (10).

Secondary endpoints are discharge from treatment and readmission to treatment (the latter is assumed to be right-censored).

Adverse events will be defined as debut of suicidal ideation, attempted suicide, debut of self-harming behaviour, severe self-harm where medical attention is indicated, hospitalisation for low weight or medical complications from low weight, admission to inpatient treatment for anorexia nervosa, involuntary gastric tube feeding, parental separation, and initiation of contact with child protective services.

Participant experiences and satisfaction with services will be assessed using the Generic Short Patient Experiences Questionnaire (GS-PEQ) (13).

The primary endpoint for the prospective study is continued morbidity, defined as being currently in treatment in specialist health care for any eating disorder. Secondary endpoints are mortality, level of education and employment status.

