Data for the retrospective part of the study will be extracted from electronic patient health records. Weight data will be extracted directly from the electronic patient health record system (DIPS). One researcher will further go manually through all records of included patients and extract dates of treatment start, adverse events, discharge and any readmission, as well as checking the record for any weight measurements recorded but not entered into the weight database. As covariates we will also extract age, sex, gender, family structure, extent of care benefits received during treatment (pleiepenging), and comorbid disorders (ICD-10 diagnoses). Another researcher will independently extract data from a random 10% subsample for control and reliability assessment of coding.

Each participant will be assigned a random case identity number, which will be used for identification in all dataset files when data is analysed. Participant national identity numbers will be stored along with the corresponding case identity number in a separate file, the identity key file. Access to the identity key file will be restricted to the project manager and researchers performing data extraction. It will also be delivered to the agencies maintaining the relevant public registries.

When extracted, data will be entered directly into a REDCap database maintained by Akershus university hospital. Access will be restricted to researchers in the project group. Data will be stored and analysed de-identified.

Data for the prospective part of the study will be acquired from the following public registries: Norwegian Patient Registry, Norwegian Cause of Death Registry, and the databases “Attachment to employment, education and welfare benefits” and “Educational attainment of the population” collated by Statistics Norway. Data will be acquired from these databases in three waves; five, ten and twenty years after the last participant initiated treatment. All registry data will be acquired, stored and analysed de-identified.

Analysis plan

Statistical analysis will be conducted in a Bayesian framework using the Stan platform through the R (14) package brms (15).

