We will evaluate whether adoption of FBT has led to faster weight normalisation by fitting a parametric survival model to the number of days until weight restoration is achieved. We will also fit models with gender, age, baseline weight, comorbid disorders and family structure as covariates, and further investigate whether any of these act as moderators of FBT compared with previous treatment. Similar parametric survival models will also be used for modelling differences in time to discharge and readmission. Differences in the rate of adverse events will be modelled using Poisson regression.

We will also evaluate differences between the cohorts in treatment course by fitting multilevel spline models to weight data with knots for every 4 weeks in treatment. Weight measurements will be nested within patients, and patients nested within cohorts. Spline models will allow for modelling non-linear weight change over the course of treatment, and the multilevel structure at the patient level will allow us to evaluate changes in heterogeneity of treatment response pre and post adoption of FBT, as well as visualise trends and heterogeneity of weight change across the course of treatment.

Analysis of prospective data will use parametric survival models or logistic or ordinal regression models, depending on the level of time specificity available in the data.

We have conducted simulations to investigate statistical power, assessing the type S (sign) and type M (magnitude) error rates, given inference based on the posterior median. We made the assumption of achieving at least a sample size of 150 patients and that implementation of FBT has led to a 10% increase in the probability of an event (i. e. weight restoration or discharge). With 1000 simulations, we estimated a type S error of 0.00 and an M error of 0.89, suggesting a very low risk of estimating the sign of the effect incorrectly and a small risk of underestimating the effect size. We conclude that the study will be adequately powered to achieve its primary aim.

The analysis will employ weakly informative prior distributions, using previous studies and other external knowledge (for instance about the biological limits of weight gain per day) to construct priors that rule out impossible areas of the parameter space (17).

ETHICAL CONSIDERATIONS

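### The primary endpoint has no rule for patients already at 95% of expected weight at treatment start, and the survival model for the primary question is stated without baseline weight

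*Combined protocol and SAP*

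**What the plan says.** The Participants and recruitment section describes the design: "This is a two-group retrospective exploratory cohort study with prospective longitudinal follow-up in public registries". It admits patients "with a primary ICD-10 diagnosis of F50.0 Anorexia nervosa or F50.1 Atypical anorexia nervosa". The only exclusion concerns patients treated in 2018-2020 who never started FBT; nothing is said about weight at entry. On size: "It is estimated that the final sample size will be approximately 200".

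The AIMS section makes the primary question one of speed: "patients achieving normalisation of weight faster than with the previously delivered family therapy". Under Endpoints and data collection, the event is "weight restoration, defined by patients having a weight measurement placing them at or above 95% of expected body weight (50. percentile) for age". It does not require a start below 95%.

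The Analysis plan then states: "We will evaluate whether adoption of FBT has led to faster weight normalisation by fitting a parametric survival model". The outcome is days until restoration. No covariates, distribution or day-0 rule are named. The next sentence adds further models with gender, age, baseline weight, comorbidity and family structure. No section says which model carries the primary conclusion.

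The data needed to close the gap are already collected. Weights come from the health record system, and a researcher will "extract dates of treatment start, adverse events, discharge and any readmission".

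**The concern.** There are two linked gaps, and the second is the larger.

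- **Risk set.** A patient at or above 95% at treatment start has nothing to restore and carries no information on speed of restoration, yet meets the event definition at once. A time of exactly 0 cannot be fitted by a lognormal, or by a Weibull with shape other than 1, so someone would have to improvise a fix after seeing the data.
- **Lead model.** Treatment was not randomised, and the event is the crossing of a fixed threshold, so distance from that threshold at the start is an obvious potential confounder. If one era's patients start closer, a model without covariates reads the difference as a treatment effect, in either direction. With adjusted and unadjusted models both fitted and neither named as primary, two analysts following the plan could report different primary answers.

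**Working it through.** **The plan's own figure.** The plan reports a type S error of 0.00 and a type M error of 0.89 for at least 150 patients and a 10% increase in event probability. This cannot be rebuilt, because the control rate, the scale of the 10%, follow-up, distribution and prior are not given. A rough bracket with 75 per cohort, reading the 10% as 50% vs 60%: SE = √(0.5×0.5/75 + 0.6×0.4/75) = 0.081, so P(wrong sign) = Φ(−0.10/0.081) ≈ 0.11. The concern does not depend on this figure.

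**Inputs from the plan.** N = 150 and 200; threshold 95%; inference on the posterior median (so wrong sign means a point estimate below HR 1); the 10% increase read as 50% vs 60% restored, giving HR = ln(0.4)/ln(0.5) = 1.32.

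**Assumed inputs.** Baseline percent of expected weight normal with SD 8; equal-sized eras; exponential times with median 240 days at a baseline of 85%; censoring at 540 days; log-hazard slope 0.05 to 0.08 per point; already-restored patients set to 7 days.

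**Share already restored.** P(Z ≥ (95 − mean)/8) is P(Z ≥ 1.25) = 11% at mean 85, P(Z ≥ 1.00) = 16% at 87, and P(Z ≥ 0.75) = 23% at 89.

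**Confounding put in.** Slope × era difference runs from 0.05×2 = 0.10 to 0.08×4 = 0.32 on the log-hazard scale. The assumed true effect is ln(1.32) = 0.28.

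**Simulation.** Maximum likelihood Weibull proportional-hazards fits with Wald 95% intervals stand in for the Bayesian models; 4,000 replicates per cell. Ranges run over the two slopes.

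| Scenario | N | No covariates | Baseline-adjusted | Adjusted, and below 95% only |
|---|---|---|---|---|
| No effect, 85 vs 87: interval falsely favours FBT | 200 | 12-16% | 3% | 3% |
| No effect, 85 vs 89: same | 200 | 38-51% | 3-4% | 3% |
| No effect, 85 vs 87: same | 150 | 10-13% | 3-4% | 3% |
| No effect, 85 vs 89: same | 150 | 30-40% | 3% | 3% |
| HR 1.32, earlier era 2 points closer: wrong sign | 200 | 26-37% | 7% | 5% |
| HR 1.32, earlier era 4 points closer: wrong sign | 200 | 62-75% | 8% | 6% |
| HR 1.32, earlier era 2 points closer: wrong sign | 150 | 29-39% | 10-11% | 8% |
| HR 1.32, earlier era 4 points closer: wrong sign | 150 | 60-74% | 11-12% | 9% |
| HR 1.32, equal eras: wrong sign | 200 | 8-10% | 7% | 5% |
| HR 1.32, equal eras: interval above 1 | 200 | 26-29% | 35-37% | 38% |

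**Large samples (200,000 patients).**

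- No effect, 85 vs 89, slope 0.08: HR 1.34 without covariates, 1.19 with exclusion alone, 0.99 with adjustment alone, 0.99 with both. Exclusion without adjustment is not enough.
- True HR 1.32: estimated as 1.25-1.28 with adjustment alone and 1.31-1.32 with both. Setting already-restored patients to anything from 0.5 to 28 days widens these to 1.22-1.31 and 1.31-1.33.

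**Sensitivity (N = 200).**

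- With the plan's own covariates (baseline kg, age, sex) in place of percent, for a 2-point (4-point) era difference: adjustment alone falsely favours FBT in 4% (4-5%) and has the wrong sign in 8% (10%). Both steps give 3% (3-4%) and 5-6% (7%).
- With Weibull shape 1.5: false-favourable 9-13% (35-49%) without covariates, against 2% (2-3%) with adjustment.
- A separate set-up (100 per cohort, median 180 days, censoring at 730 days, already-restored patients set to day 1, no covariates) agrees in direction. Under no effect, shares already restored of 10% (earlier) and 20% (FBT) give HR 1.11, and 20% and 10% give 0.88. A true 1.3 is estimated as 1.21 with 10% in both cohorts and 1.18 with 20%. Removing those patients returns 0.99-1.01 and 1.29-1.31.

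**The case against.** The strongest reply is that the remedy for the larger problem is already in the plan: the baseline-adjusted models will be fitted, and a reader of the report would see both. The plan labels no model primary, so the lead status of the model without covariates is inferred from sentence order. The study calls itself exploratory, the word restoration suggests a start below target, and the spline models compare weight course without a time-zero problem. A time of 0 would also show itself at model fitting.

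The size is open to challenge too. At 4 points and slope 0.08 the confounding put in (0.32) exceeds the true effect (0.28), so a high wrong-sign rate is close to built in. With a 1-point era difference the model without covariates falsely favours FBT in 6-7% of runs and has the wrong sign in 16-18%. With both means at 82, about 5% start at or above 95% and dilution nearly vanishes (1.31 with adjustment alone, 1.33 with both). Restricting the risk set also narrows the population in a study that includes atypical cases.

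Most of this stands as a limit on size and on what the risk-set rule adds. It does not close the gap: no section defines who is at risk of restoration or says which survival model leads.

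**Conclusion.** The concern holds and should be fixed. Confidence is high that the gap exists and low about its size, because the plan gives no baseline weight distribution and every rate above rests on assumed means, spread and slope.

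The choice of lead model matters most. If the eras differ by a few points at the start, the model without covariates can mislead in either direction, while the covariates already listed remove nearly all of the problem. Adjustment also supplies almost all of the power gain when the eras do not differ. The risk-set rule is the smaller step: it removes the residual dilution and settles times of 0 in advance.

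**What to change.** 1. Make the already planned model with baseline weight, age and gender/sex (or with baseline percent of expected weight) the primary analysis of time to restoration. Report the model without covariates as supportive.
2. Restrict the risk set for this endpoint to patients below 95% at a baseline weighing within a stated window around treatment start. Report the number excluded by era, keep those patients for all other endpoints, and state a rule for patients with no weighing in the window.

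The cost is SAP wording; no new data are needed. Step 1 promotes an analysis already planned. Step 2 has a price: the question narrows to patients who start below 95%. The analysed sample falls by roughly 10-20% (200 to 160-180, or 150 to 120-135; 11-17% in these simulations). The standard error of the log hazard ratio rises by 7-13% at N = 200, from about 0.16 to 0.17-0.18.

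### The primary weight-restoration threshold is set by age with no height formula, and height is not extracted, so as written it marks a different degree of recovery in tall and short patients

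*Combined protocol and SAP*

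**What the plan says.** Under Endpoints and data collection, weight restoration is a weight measurement "at or above 95% of expected body weight (50. percentile) for age given Norwegian population norms". The sentence ends "following established definitions of weight restoration (10", that is, with a citation of reference 10. No formula is written out.

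The same section lists the data. Weights come from the electronic record system, and one researcher reads every included record, which includes "checking the record for any weight measurements recorded but not entered into the weight database". That reading also yields dates of treatment start, adverse events, discharge and readmission. The covariate list begins "As covariates we will also extract age, sex, gender, family structure" and goes on to care benefits and comorbid diagnoses. Height is not on any of these lists.

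The Analysis plan uses the endpoint by "fitting a parametric survival model to the number of days until weight restoration is achieved". On adjustment it says "We will also fit models with gender, age, baseline weight, comorbid disorders and family structure as covariates". Height is absent there too.

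**The concern.** The Background treats normal eating and normal weight status as the main goal of treatment, and the Aims ask whether patients reach normal weight sooner under FBT. Whether a given weight is normal for an adolescent depends on height as well as age. A threshold fixed by age alone is passed by a tall patient who is still light for her height. A short patient must go beyond the weight expected for her height before she counts as restored.

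Three things are at stake: what the primary event means, the day on which it is recorded, and how many patients already satisfy it when treatment starts. The last matters because Participants and recruitment admits atypical anorexia (F50.1) alongside F50.0, so patients who start close to the threshold are plausible. If height is not collected, none of this can be repaired or even examined at analysis.

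**Working it through.** The plan gives no figure on this point to reproduce. The check has a text part and an arithmetic part.

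**Text.** The endpoint names one index variable, age. The extraction list contains weight, age and sex but not height. The data can therefore support a weight-for-age threshold, by sex if the norms allow it. They cannot support a height-adjusted one, whatever reference 10 says.

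**Inputs.** The 95% cut-off is from the protocol. The rest is assumed: median height H = 165 cm (160 to 170 also tried); normally distributed height with SD 6 cm within an age and sex group (5 to 7 also tried); expected weight proportional to height squared; and a patient of median height expected to have the median weight.

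**Implied threshold.** With W the median weight for age, the threshold is 0.95 × W. The height-adjusted expected weight at height h is W × (h/H)². As a percentage of that, the threshold is 95 × (H/h)², and W cancels.

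| Height (H = 165 cm) | Calculation | Threshold, % of height-adjusted weight |
|---|---|---|
| 153 cm (-2 SD) | 95 × (165/153)² | 110.5 |
| 159 cm (-1 SD) | 95 × (165/159)² | 102.3 |
| 165 cm | 95 × 1 | 95.0 |
| 171 cm (+1 SD) | 95 × (165/171)² | 88.5 |
| 177 cm (+2 SD) | 95 × (165/177)² | 82.6 |

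At 6 cm below and above the median, H = 160 gives 102.5 and 88.3, and H = 170 gives 102.1 and 88.6. The choice of H hardly matters.

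**Patients at a fixed degree of recovery.** A patient at s% of height-adjusted weight meets the threshold when h ≥ H × √(95/s).

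- s = 90: h ≥ 165 × √(95/90) = 169.5 cm, which is 4.5/6 = 0.75 SD above the median. Probability of counting as restored: about 23% (18% for SD 5 cm, 26% for SD 7 cm).
- s = 100: not restored if h < 165 × √0.95 = 160.8 cm, which is 4.2/6 = 0.70 SD below the median. Probability: about 24% (20% to 28%).
- s = 85: h ≥ 165 × √(95/85) = 174.4 cm, which is 9.4/6 = 1.57 SD above the median. Probability: about 6%.

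The first and third lines also apply at baseline. A patient who starts at 90% or 85% of height-adjusted weight already meets the threshold in about 23% or 6% of cases, through height alone.

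**The case against.** **The citation may settle it.** The endpoint is an expected body weight taken from a cited source, and that source may adjust for height. If so, the fault is brief wording. This stands as a limit: the documents do not show that the authors intend weight-for-age. It does not remove the point, because a height-adjusted endpoint would need an input that the plan does not collect.

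**The 23% and 24% are not misclassification rates.** A reader might infer that about a quarter of the cohort is wrongly classified. The documents do not support that. The figures describe hypothetical patients held at 90% or 100% under assumed heights, and the cohort's weight distribution is not given. In a time-to-event analysis patients move through these values, so much of the effect is a shifted date.

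**The comparison may be barely affected.** A reader might infer that the FBT contrast is biased. That needs height for age to differ between cohorts, and nothing in the documents shows that it does. A simulation with heights balanced between cohorts supports the objection. It assumed 180 patients, a norm of 56 kg at 165 cm, height SD 5 to 7 cm, mean baseline 82 to 85% of height-adjusted weight, weight gain 1.3 times faster under FBT, a lognormal model, and exclusion of patients already above the threshold. The mean log time ratio differed by at most 0.016 between the two definitions. Without adjustment, the SD of the estimate was 5 to 26% larger under weight-for-age. With adjustment for baseline weight, which the plan intends, it ranged from 4% larger to 17% smaller. So the planned adjustment absorbs most of the timing noise when heights are balanced. It does not change which event is timed, and 5 to 17% of simulated patients were above the threshold at baseline, against about 1.5 to 8% with height adjustment.

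**Sex.** The definition does not mention sex, and a reader might infer norms pooled over both sexes. Sex is extracted and sex-specific norms are not excluded, so this needs only a clarifying word.

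**Conclusion.** The concern holds in a limited form. As written, the retrospective primary endpoint is a weight-for-age threshold. If a height-adjusted one is meant, its formula and its essential input are both missing. Under the assumed heights, the same 95% stands for anything from 84.6% to 107.5% of height-adjusted weight between the 5th and 95th percentiles of the implied threshold (SD 6 cm). These sizes rest on assumptions outside the documents; the direction does not.

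The damage is mainly to what restoration means, to the event date, and to the number of patients who qualify at baseline. Bias in the treatment contrast is possible but not shown. In a non-randomised before-and-after comparison, balance in height for age is not guaranteed, and it cannot be checked if height is never collected. Because this is the primary endpoint and the listed data cannot repair it later, it should be corrected rather than only noted.

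**What to change.** - Write out the expected-weight formula, specific to age, sex and height. One option is the Norwegian median BMI for age and sex multiplied by height squared at the date of weighing. Another is the formula in reference 10, if that is height-adjusted. Keep the 95% cut-off.
- Add all recorded heights, with dates, to the extraction list. Where none exists for a weighing date, use the nearest recorded height or interpolate.
- State how patients already at or above the threshold at baseline enter the survival analysis.
- Report weight-for-age as a sensitivity analysis, and compare height for age between cohorts.

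The cost is modest but more than one extra field, since height is a repeated measure. Every included record is already read by hand, so most of the work fits into that reading. The Study timeline starts extraction for each participant at consent, so records read before the change would need a second look. Some heights will be missing or interpolated; the documents do not say how often height was recorded. The change also needs an amendment approved by the ethics committee.

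### Two adverse events count only as a first occurrence, but no listed variable records prior history and no at-risk set is defined, so the cohort comparison on these two items can be biased

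*Combined protocol and SAP*

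**What the plan says.** - **Definition.** Under Endpoints and data collection, the list of nine adverse events begins: "Adverse events will be defined as debut of suicidal ideation, attempted suicide, debut of self-harming behaviour". Two of the nine, suicidal ideation and self-harming behaviour, are restricted to a debut. Attempted suicide and severe self-harm carry no such restriction.
- **Data.** In the same section, one researcher reads the full record of every included patient to "extract dates of treatment start, adverse events, discharge and any readmission". The covariates are then listed: "As covariates we will also extract age, sex, gender, family structure, extent of care benefits received during treatment (pleiepenging), and comorbid disorders (ICD-10 diagnoses"). No item covers suicidal ideation or self-harm at or before treatment start. ICD-10 comorbidity is at most an indirect proxy.
- **Analysis.** The Analysis plan says only: "Differences in the rate of adverse events will be modelled using Poisson regression". It states no at-risk set, no exposure offset, no covariates for this model, and no rule on whether event types are pooled. The covariate-adjusted models are described for weight restoration.
- **Role and population.** Aims makes it a secondary question "whether there have been changes in the rates of adverse events and readmissions". Participants and recruitment says: "Eligible participants are all patients initiating treatment during the years 2015-2020", with no restriction on prior suicidality or self-harm.

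**The concern.** A patient who starts treatment already suicidal or self-harming cannot have a debut of that symptom. If such patients stay in the denominator, each contributes a zero that says nothing about the treatment. The two cohorts are separated by calendar time and are not randomised, so equal history at entry cannot be taken for granted. A difference in history alone would then produce a difference in the debut rate, and a real difference in risk could be hidden.

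The gap is in the data as well as the wording. If history is seen during record review but not stored, the analysts can neither correct the denominator afterwards nor report whether the cohorts differed at entry.

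**Working it through.** The documents give no adverse event rates, no entry prevalence and no power for adverse events, so there is no figure of the plan's own to reproduce. What follows is an illustration.

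**Inputs.** From the protocol: two debut-defined events out of nine, and a sample of at least 150 (Analysis plan). Assumed: an equal split of 75 per cohort, entry prevalences pA and pB, and the same expected number of debuts h per patient without history in both cohorts.

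**Step 1, debut items with all patients in the denominator.** Expected debuts per patient are (1-p)h, so with equal exposure the apparent ratio B/A is

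(1-pB)h / (1-pA)h = (1-pB)/(1-pA),

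whatever h and the sample size are. The true ratio is 1.00.

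| pA | pB | Apparent ratio | Ratio among patients without history |
|---|---|---|---|
| 20% | 30% | 0.70/0.80 = 0.875 | 1.00 |
| 20% | 40% | 0.60/0.80 = 0.75 | 1.00 |
| 30% | 50% | 0.50/0.70 = 0.71 | 1.00 |
| 10% | 50% | 0.50/0.90 = 0.56 | 1.00 |

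**Step 2, in events.** With h = 0.2 and 20% v 40%: cohort A has 75 × 0.80 × 0.2 = 12.0 expected debuts and cohort B has 75 × 0.60 × 0.2 = 9.0. Over all patients the ratio is 9.0/12.0 = 0.75. Over the 60 and 45 patients at risk it is (9.0/45)/(12.0/60) = 1.00.

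**Step 3, masking.** At the same prevalences a true ratio of 1.33 would appear as 1.33 × 0.75 = 0.998, about 1.00.

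**Step 4, pooled with attempts and severe self-harm.** Let s be the expected number of these unrestricted events per patient with history and s0 per patient without. The expected count per patient is f(p) = (1-p)(h+s0) + p·s. With assumed h = 0.3, s0 = 0.05, pA = 20%, pB = 40% and no other events:

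- s = 0.05: 0.23/0.29 = 0.79
- s = 0.20: 0.29/0.32 = 0.91
- s = 0.35: 0.35/0.35 = 1.00
- s = 0.60: 0.45/0.40 = 1.13

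The direction reverses once s exceeds h + s0.

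**Step 5, history not checked.** If a share m of patients with history have a pre-existing symptom coded as a debut when it is first noted in treatment, the expected count per patient becomes (1-p)h + p·m. The added term is larger in the cohort with more history, so it pushes the ratio up, and above 1 once m exceeds h.

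**The case against.** Several objections stand and limit the point.

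- **The denominator is not stated.** A reader might infer that all patients enter the rate. The protocol does not say so; it merely states no restriction. The supportable statement is that the at-risk set is undefined.
- **The record reviewer can see history.** A reader might infer that the at-risk group can never be formed. That is too strong: a debut can hardly be coded without looking for earlier occurrence, and all records are read, with independent extraction in a random 10%. What is missing is a stored variable. Without one, what the reviewer saw does not reach the analysis.
- **Direction.** A reader might infer that the more severely ill cohort will look safer. That holds only for the two debut items, only if history is unequal, and only if debuts are coded correctly. Steps 4 and 5 show that pooling or miscoding can reverse it. The documents give no evidence that the cohorts differ in history, although without the variable the study could not show whether they do.
- **Exposure.** The formula assumes equal exposure. The protocol itself asks whether time to discharge changed, so this is not assured, and the unstated offset affects all nine events.
- **Size beside sampling error.** With 12 v 9 events, the standard error of the log ratio is √(1/12 + 1/9) = 0.44, giving a 95% interval of about 0.32 to 1.78 around 0.75. The bias at a 20-point imbalance is small beside that. It is still systematic and cheap to remove.
- **Counting new-onset events is legitimate.** This is correct. The debut definition can stay; it needs a matching denominator.

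**Conclusion.** The point holds in conditional form. Two of nine adverse events can occur only in patients without a given history, no listed variable records that history, and the analysis names no at-risk set. If all patients are used and entry history differs, the apparent ratio for these items departs from a true ratio of 1.00: 0.875 at 20% v 30%, 0.75 at 20% v 40%, 0.71 at 30% v 50%. These figures rest on assumed prevalences, equal debut risk among patients without history, equal exposure and correct coding of debuts. For a pooled count the illustrations run from 0.79 to 1.13 with event rates within each history group the same in both cohorts, so no direction can be claimed.

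The issue concerns a secondary aim of an exploratory study and does not touch weight restoration or the registry endpoint. It is worth correcting because data that are not stored at extraction cannot be supplied by the analysis.

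**What to change.** 1. In the planned manual record review, add two yes/no fields: any suicidal ideation at or before treatment start, and any self-harm at or before treatment start. Include both in the 10% reliability subsample.
2. Analyse each debut item only among patients without that particular history, with time in treatment as exposure, or as time to first event.
3. Report the two debut items separately from the other adverse events.
4. Report the entry prevalence of each history item by cohort.

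Counting recurrence or worsening in patients with history is optional. It would require graded judgement from routine notes across two periods and is not part of the required change.

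The cost is two database fields filled during a review already planned, and some precision. Fewer patients are at risk (60 and 45 instead of 75 and 75 in the illustration), which widens the intervals for the rate or risk of each debut item. Separate reporting also leaves fewer events in each comparison.
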